- j) Respiratory – Pleural effusion, atelectasis, cough, dyspnea.
- k) **Musculoskeletal – Arthralgias.**

2. Methotrexate

Toxicities: In this setting, mucositis is the primary toxicity related to methotrexate. In the setting of renal or hepatic dysfunction, where there is impaired clearance of the medication, methotrexate may contribute to delayed neutrophil engraftment. Methotrexate may cause an elevation in serum transaminase.

Regimen B: Unrelated umbilical cord blood recipients

3. Cyclosporine

See section 11 for information about administration and dosage adjustments. Side effects are generally reversible, and may include renal insufficiency, hypomagnesemia, paresthesias, tremor, seizures, visual disturbances, paresis, disorientation, depression, confusion, somnolence, coma, nausea, hypertension, hemolytic-uremic syndrome, hyperglycemia, gynecomastia, and hypertrichosis. (See Standard Practice Manual)

4. Mycophenolate Mofetil (MMF) – See section 11 for information about administration and dosage adjustments.

a) Description

MMF is the morpholinylethylester of mycophenolic acid (MPA) and reversibly inhibits inosine monophosphate dehydrogenase, particularly the type II isoform that

is more prominent in activated lymphocytes. As a result of the inhibition of de novo purine synthesis, proliferation of B and T lymphocytes is blocked and antibody production is inhibited.

b) Storage and Administration

MMF is available in an oral and an intravenous formulation. The oral formulation is supplied in 250mg hard gelatin capsules and can be stored at room temperature. MMF for IV administration is supplied as a lyophilized powder in a glass vial containing the equivalent of 500mg.

c) Side Effects and Toxicity

Precautions: MMF has been studied extensively among patients after nonmyeloablative HCT. Previous clinical studies in patients after allografting suggest that the principal adverse reactions associated with the administration of MMF include nausea, vomiting, neutropenia, diarrhea, and on one occasion bloody diarrhea. In the setting of marrow transplantation, several etiologic factors may contribute to alterations in gastrointestinal and hematologic parameters. MMF has an increased incidence of digestive system adverse events, including GI tract ulceration, and hemorrhage (3% of patients receiving MMF). GI tract perforations have rarely been observed. Most patients in these studies were also on other drugs known to be associated with these complications. Up to 2% of patients receiving MMF for prevention of rejection developed severe neutropenia (ANC <500). The development of neutropenia may be related to MMF itself, concomitant medications, viral infections or some combination of these causes. MMF dose adjustments will be made if clinically indicated if in the opinion of the attending physician, no other cause is thought to be responsible for the abnormality. These adjustments should be discussed with the principal investigator and documented in the medical records and the clinical reporting form (CRF).

16. EBV Monitoring and Treatment

Patients will have EBV by PCR plasma samples collected once a week until day 100 following transplantation. If there is documented evidence of rising copy number of EBV by PCR, monitoring will increase to twice per week through day 100 following HCT. EBV monitoring by PCR will be done every other week from Day 101 until Month 6. If there is evidence of a rising copy number, the frequency of the monitoring will be increased to once or twice a week as clinically indicated according to institutional standard.

- A) Patients who develop a viral load of > 1000 copies per mL plasma will receive further individualized monitoring, evaluation by Transplant Infectious Disease service according to institutional practice and/or therapy as per institutional standards and Infectious Disease recommendations.
- B) If the patient develops increasing viral load, it is suggested that he or she be treated with either preemptive Rituximab 375 mg/m² IV weekly x 4 weeks or an EBV reactivation protocol according to local institution practice and ID recommendation. It is suggested that subjects who develop EBV reactivation and/or asymptomatic increasing viral load by PCR undergo flow cytometry of the peripheral blood and CT or MRI imaging of chest, abdomen, and pelvis to assess the development of lymphadenopathy, organomegaly, or other evidence of the development of PTLD. Whenever possible, the clinical diagnosis of PTLD should be confirmed by tissue biopsy.

17. DATA AND SAFETY MONITORING PLAN AND ADVERSE EVENT REPORTING

17A. Monitoring the Progress of Trials and the Safety of Participants

The principal investigators (PI) monitor multi-institutional clinical trials, with oversight by the Medical Monitor, a Data Safety and Monitoring Board (DSMB), the Data and Safety Monitoring Committee (DSMC) and the Institutional Review Board (IRB). The PI reviews outcome data for each individual patient on an ongoing basis.

This multi-center protocol has a DSMB responsible for monitoring patient safety by reviewing protocol data and safety endpoints. The DSMB meets twice a year and all outcome data is reviewed including all adverse events reported to the coordinating center (FHCRC) along with those officially reported to the FHCRC IRO. The DSMB confirms that the trial has not met any stopping rules and reviews any patient safety problems necessitating discontinuation of the trial. A report from the DSMB is submitted to the FHCRC IRB, the IND sponsor, the DSMC Chairman, Protocol Office, and the trial coordinators/local PIs of this protocol. The DSMB will discontinue the review of outcomes when this protocol is closed to accrual. Furthermore, the FHCRC also has a DSMC that reviews the progress of the protocol with respect to the monitoring plan at the time of each annual renewal. As with initial review, annual IRB review and approval is also required.

Flow of information concerning clinical trial participants originates with the clinicians and nurses in the clinic or referring clinicians at other institutions and is transmitted to the FHCRC Trial Coordinator. At the FHCRC, health care providers and rotating attending physicians assess patients and record their observations regarding toxicity and response outcomes in the medical record. Thus, multiple health care providers provide independent observations and participate in monitoring this trial. The PI may be a clinician for some patients entered on this trial. However, assessments are the sum total of the primary health care provider (fellow or physician assistant), floor or outpatient nurse and the PI or other attending clinician involved with the patient avert a possible conflict of interest having the PI as the attending clinician for protocol patients. If determination of adverse events is controversial, co-investigators will convene on an ad hoc basis as necessary to review the primary data and render a decision.

17B. Adverse Event Definitions

a. Adverse Event

An Adverse Event (AE) is any untoward medical occurrence in a clinical investigation subject administered a medicinal product; the event does not necessarily have a causal relationship with study drug administration or usage. An adverse event can therefore be any unfavorable and unintended sign (including an abnormal laboratory finding), symptom, or disease temporally associated with the use of a medicinal product, whether or not considered related to the medicinal product.

b. Serious Adverse Event

A serious adverse event (SAE) is defined as an untoward medical occurrence that results in any of the following outcomes:

- Death.
- Life-threatening situation (ie, with an immediate risk of death from the event as it occurred but not including an event that, had it occurred in a more serious form, might have caused death).
- In-patient hospitalization or prolongation of existing hospitalization. Inpatient hospitalization comprises formal admission to a hospital for medical reasons, for any length of time, whether or not hospitalization extends overnight. However, hospital admissions for administration of the study drug, procedures required by the study protocol, or tumor-related diagnostic procedures are not considered serious.

- Persistent or significant disability/incapacity or substantial disruption of the ability to conduct normal life functions.
- Congenital anomaly/birth defect.
- An important medical event that requires intervention to prevent one of the above outcomes.

c. Unexpected Adverse Event

An unexpected adverse event is defined as an event that has a nature or severity, or frequency that is not consistent with the applicable investigator brochure. "Unexpected," as used in this definition, refers to an adverse drug experience that has not been previously observed and reported rather than an experience that has not been anticipated based on the pharmacological properties of the study drug.

17C. Monitoring and recording AEs

Adverse events will be collected and graded using the **modified (for HCT) NCI Common Toxicity Criteria (Appendix G of the protocol)**. All grade 3 and 4 adverse events (or highly unusual grade 2 adverse events), which occur from the start of study treatment (pre-transplant conditioning) through day 100 post-transplant, will be assessed by the investigator or qualified designee and recorded in the CRF, whether or not attributed to the study intervention. Adverse events that occur between the start of conditioning and day 30 will be assessed separately to identify early regimen related toxicities. The investigator should attempt to establish a diagnosis of the event on the basis of signs, symptoms and/or other clinical information. In such cases, the diagnosis should be documented as the adverse event and/or serious adverse event and not described as the individual signs or symptoms. The following information should be recorded:

- Description of the adverse event using concise medical terminology
- Description as to whether or not the adverse event is serious
- The start date (date of adverse event onset)
- The stop date (date of adverse event resolution)
- The severity (grade) of the adverse event
- A description of the potential relatedness of the adverse event to study drug or a study procedure
- The action taken due to the adverse event
- The outcome of the adverse event

The adverse event reporting in this multi-institution clinical trial will follow both the sponsor and IRB guidelines for serious adverse event (SAE) reporting. The classification of an adverse event determines what reporting procedure to follow for reporting the adverse event. (See **Table 2 and 3**).

17D: Grading of the severity of an Adverse Event

Adverse events will be graded according to CTCAE criteria. If a CTCAE criterion does not exist, the investigator should use the grade or adjectives: Grade 1 (mild), Grade 2 (moderate), Grade 3 (severe), Grade 4 (life-threatening), or Grade 5 (fatal) to describe the maximum intensity of the adverse event.

Attribution of Adverse Event

Association or relatedness to the study agent will be assessed by the investigator as follows:

- Definite: The event follows a reasonable temporal sequence from exposure to the investigational agent, has been previously described in association with the investigational agent, and cannot reasonably be attributed to other factors such as the patient's clinical state, other therapeutic interventions or concomitant medications; AND the event disappears or improves with withdrawal of the investigational agent and/or reappears on re-exposure (e.g., in the event of an infusion reaction).
- Probable: The event follows a reasonable temporal sequence from exposure to the investigational agent and has been previously described in association with the investigational agent OR cannot reasonably be attributed to other factors such as the patient's clinical state, other therapeutic interventions or concomitant medications.
- Possible: The event follows a reasonable temporal sequence from exposure to the investigational agent, but could be attributable to other factors such as the patient's clinical state, other therapeutic interventions or concomitant medications.
- Unlikely: Toxicity is doubtfully related to the investigational agent(s). The event may be attributable to other factors such as the patient's clinical state, other therapeutic interventions or concomitant medications.
- Unrelated: The event is clearly related to other factors such as the patient's clinical state, other therapeutic interventions or concomitant medications.

For general AE assessment, an AE is considered related if it is assessed as definitely, probably, or possibly related; unrelated if it is assessed as unlikely related or unrelated. For determination of IND safety reporting, AE attribution will be assessed according to the suspected adverse reaction definition described in 21 CFR 312.32 as an AE for which there is a reasonable possibility that the drug caused the adverse event where "reasonable possibility" means there is evidence to suggest a causal relationship between the drug and the AE. Suspected adverse reactions that are both serious and unexpected will be reported to the FDA as an IND safety report, in accordance with regulations under 21 CFR 312.32.

17E: Adverse Event Reporting Period

All grade 3 and 4 adverse events (or highly unusual grade 2 adverse events), which occur from the start of study treatment (pre-transplant conditioning) through day 100 post-transplant, will be assessed by the investigator or qualified designee and recorded in the CRFs, whether or not attributed to the study intervention. AEs with an onset date prior to the start of study treatment will not be recorded, except in the case of clinically significant worsening of the AE during the specified monitoring time frame. The end of the adverse event reporting period occurs through day 100 post-transplant, or when any ongoing drug-related adverse events and/or serious adverse events have resolved or become stable. A subject withdrawn from the study because of an adverse event must be followed until the clinical outcome from the adverse event is determined.

All adverse events reportable to the IRB will be collected according to current reporting FHCRC IRB Policies for Reportable Events. Definitions, instructions and forms associated with reportable events can be found on the FHCRC's Institutional Review Office (IRO) extranet website: <http://extranet.fhcrc.org/EN/sections/iro/irb/ae.html>. All investigators must report adverse events to their respective IRB as locally mandated.

All events which in the opinion of the PI are (1) unexpected, and (2) related or possibly related to the research and (3) serious or suggest that the research places research participants or others at a greater risk of physical or psychological harm than was previously known or recognized will be submitted to the IRB within 10 calendar days (see Tables 2, 3, and 4 below). In addition, all serious adverse events are reported to the IRB at the time of annual renewal. The PI for a study is responsible for this reporting and the IRO assures adverse event reporting on an annual basis. The PI in the annual application for grant continuation will summarize reports of toxicities. Furthermore, stopping rules and interim analysis provides an additional safeguard for adverse event analysis and reporting in this protocol. All collaborating PIs have fulfilled all NIH requirements for training in human subject's protection.

The FHCRC PI and research staff will meet regularly to review all reported events. If the event meets FHCRC IRB current reporting obligations, it will be sent to the FHCRC IRB. After the FHCRC IRB has reviewed the event report it will be disseminated to all participating sites/investigators, the DSMB, and the study sponsor.

When a patient experiences disease recurrence or graft failure and goes on to further treatment off protocol, adverse events will no longer be collected with the exception of death.

Patients enrolled in this study are receiving treatments that are generally associated with high rates of expected adverse events (outlined in **Appendix I**).

17.F. Reporting to Coordinating Center and Fred Hutch IRB

For patients being cared for at the FHCRC, health care providers communicate with the PI or research staff as events occur triggering subsequent reporting. For patients not being cared for at the FHCRC the outside facilities communicate with the PI or research study staff for these reporting purposes.

As FHCRC is the coordinating center, all reportable events will be collected by the FHCRC PI and/or study staff for submission to FHCRC IRB. All reportable events should be submitted to the coordinating center on the relevant FHCRC IRB forms. (See **Tables 2 and 3** for FHCRC IRB Reporting Policies and Forms for Reporting)

Table 2 FHCRC IRB Policies for Reportable Events (Relevant FHCRC policies include, but are not limited to the following documents. Please also refer to the FHCRC IRO website.)

| | | |
|-----------------|--|---|
| IRB Policy 2.6 | Unanticipated Problems Involving Risks to Subjects or Others (Adverse Events) | http://extranet.fhcrc.org/EN/sections/iro/irb/ae.html |
| IRB Policy 1.9 | Noncompliance with the Office of the Director's Human Research Protection Program Policy | http://extranet.fhcrc.org/EN/sections/iro/irb/ae.html |
| IRB Policy 1.11 | Reporting Obligations for Principal Investigators | http://extranet.fhcrc.org/EN/sections/iro/irb/policy/ |
| IRB Policy 2.2 | Continuing Review | http://extranet.fhcrc.org/EN/sections/iro/irb/policy/index.html |
| IRB Policy 1.13 | Investigational New Drugs (IND), Biologics and Investigational Device Exemptions (IDE) | http://extranet.fhcrc.org/EN/sections/iro/irb/policy/index.html |

Table 3 Fred Hutch IRB Forms for Reporting

| | |
|--|---|
| Adverse Event Reporting Form | http://extranet.fhcrc.org/EN/sections/iro/irb/forms/index.html |
| Expedited Reporting Form for Unanticipated Problems or Noncompliance | http://extranet.fhcrc.org/EN/sections/iro/irb/forms/index.html |

17.G Research Site Reporting Requirements to Sponsor

Classification of an event as serious or non-serious determines the reporting procedures to be followed by the site for reporting the event to the Sponsor.

The information in the Institution-Sponsored IND SAE Reporting Form (**see Appendix E**) must match or be reconciled with the information recorded in the adverse events section of the CRF and study database. For example, the same adverse event term should be used on both forms.

All SAEs must be reported to the Sponsor from the time of study drug administration until SAE duration as outlined in the protocol. SAEs that occur after the study-specific informed consent is signed but prior to the first dose of the investigational agent will be collected only if they are considered by the investigator to be causally related to the study required procedures. SAEs will be reported by the PI or Research Nurse to the Sponsor according to the timelines described in **Table 4**.

Table 4: Reporting Requirements to Sponsor for Adverse Events

| Classification | Reporting time | Reporting Time | Reporting Action | Contact Information |
|-----------------------------|-------------------------------|--|--|---|
| Serious Adverse Event (SAE) | Fatal or life-threatening | Within 24 hours of research team* awareness | Email notification to sponsor and to both the Sponsor's Medical Monitor and the PI | IND Sponsor's Medical Monitor email: [contact] IND Sponsor's email: [contact] PI's Email: [contact] |
| | All SAEs | Within 2 business days of research team* awareness | Submit completed IND SAE Reporting Form signed by PI or designated sub-Investigator to both the IND Sponsor and the PI | IND Sponsor's email: [contact] PI's Email: [contact] |
| Non-serious Adverse Event | Per CRF completion guidelines | | Record information on appropriate CRFs | N/A |

*Research team is defined as the individuals listed on the delegation of authority log. Physicians listed on the study's delegation of authority log as transplant service attending physicians delegated authority to administer informed consent will not be considered part of the research team unless additional responsibilities related to the conduct of the study have been delegated to them by the Principal Investigator.

17H: FHCRC Sponsor Reporting Requirements

The sponsor assumes responsibility for IND safety reporting to the FDA and participating investigators, in accordance with regulations under 21 CFR 312.32.

Each serious adverse event report received from the investigator will be evaluated by the Medical Monitor who will assess the seriousness of the event (see Section 17B.b), the expectedness of the event (see Section 17.B.c), and the relationship to participation in the study (see Section 17.D). For regulatory reporting purposes, the Sponsor will determine expectedness relating to treosulfan using safety information specified in the treosulfan investigator brochure. An event will be classified as related if either the investigator or the Sponsor determines that the event may be related to the study drug.

The Sponsor or its designee will provide all investigators with a safety letter notifying them of an event that meets FDA IND Safety Reporting criteria. Investigators will be requested to provide written notification of safety report to the FHCRC IRB as soon as is practical, consistent with IRB requirements.

17I. Plans for Assuring that any Action Resulting in a Temporary or Permanent Suspension of an NCI-funded Clinical Trial is Reported to the NCI Grant Program Director Responsible for the grant

This clinical research trial is associated with an Investigational New Drug (IND). Any temporary or permanent suspension, as determined by the PI, IRB, IND Sponsor, or DSMC, of this clinical research trial will be reported to the NCI grant program director by the PI.

17J. Plans for Assuring Data Accuracy and Protocol Compliance

The study has dedicated research staff who follow patients to confirm eligibility; reporting of adverse events; reporting of events, which are part of the safety-monitoring plan, and protocol adherence. The PI, data coordinators, and research staff are responsible for review and maintenance of all patient records to ensure data integrity and protocol adherence.

At the FHCRC, health care providers and rotating attending physicians assess patients and record their observations in the medical record. This documentation is extracted by study research staff via chart review and entered into an electronic Case Report Forms (CRF's). The study staff also continue to follow patients after day 100, review source documentation, and complete CRFs at 6 months, 1 year, 1.5 years, and then annually per protocol. The CRFs are printed directly from the database, and the PI reviews the CRFs and the primary source documents for data accuracy. After the CRFs are verified, they are signed by the PI. Thus, multiple health care providers provide independent observations and participate in assessments on this trial.

Outside center clinical trial participant's information is transmitted to the FHCRC Trial Coordinator. Clinical outcome data are summarized and transmitted from collaborating centers as CRFs. CRFs from external sites are verified and signed by the local investigators at that site. The CRFs are generated from the collaborating centers at protocol defined time points. When possible, primary source documents regarding patient outcomes are collected with patients' names removed and replaced by Unique Patient Numbers (UPNs). The data are incorporated into a central database by the data manager. Collaborating sites send signed consents, eligibility forms, and CRFs with source documents demonstrating eligibility, treatment, and serious adverse events (if applicable) to the study staff. These are reviewed for eligibility, adherence to the protocol, accuracy, and completeness by the study staff.

The study is monitored under the FHCRC Monitoring Plan. The FHCRC Data and Safety Monitoring Plan details the full scope and extent of monitoring and provides for immediate action in the event of the discovery of major deviations.

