| Relapse | 17 | 23 | 26 |
| TRM | 2 | 2 | 2 |

2d. Treosulfan Pharmacokinetics

Studies have demonstrated highly predictable PK in adult patients; however, limited data are available for pediatric patients. In addition, very little data is available on the relationship between treosulfan exposure and HCT outcomes including early toxicities and engraftment. Van der Stoep recently published on treosulfan pharmacokinetics and the drug's relationship with regimen-related toxicity and early clinical outcome in 77 pediatric patients with hematological malignancies (n=12) or non-malignant diseases (n=65) who underwent HCT. Conditioning consisted of treosulfan, fludarabine, +/- thiotepa (n=52) followed by HLA-matched sibling n=27, matched URD ($\geq 9/10$; n=36), or haploidentical (n=14) grafts. Hematopoietic cell sources varied and included bone marrow (n=50), PBSC (n=20), cord blood (n=6), and bone marrow plus cord blood (n=1). Van der Stoep and colleagues reported low intra-patient variability (13.9%) but high inter-patient variability [56%; <1-year old, (n=12) and 33%; ≥ 1 to 21 years of age (n=65)] among 77 pediatric patients. This is in contrast to that seen in adult patients where there is low intra- and low inter-patient variability. In addition, high treosulfan exposure ($>1650 \text{ mg}^*\text{h/L}$) was associated with an increased risk of developing grade 2 or higher mucositis [OR 4.40; 95% CI 1.19–16.28, p=0.026], increased risk of skin toxicity, including erythematous rash and skin exfoliation, [OR 4.51; 95% CI 1.07–18.93; p=0.040], and increased risk of developing multiple toxicities [OR 4.52; 95%CI 1.32–15.53, p=0.016] compared to the lower exposure ($<1350 \text{ mg}^*\text{h/L}$) group. The authors highlighted that their study included a heterogeneous group of diseases and additional data in more homogeneous and single disease groups with longer follow up are needed in order to better understand the relationship between AUC and long-term outcomes. We plan on collecting PK samples on patients enrolled on this clinical trial in order to gain a better understanding whether the exposure to treosulfan AUC for pediatric patients with nonmalignant diseases impacts engraftment and both acute and long-term toxicities. This information will help guide future studies using treosulfan-based conditioning in patients with non-malignant diseases.

3D. Fludarabine

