APPENDIX G continued

| Grade | | |
|--|---|--|
| Adverse Event | 3 | 4 |
| GASTROINTESTINAL continued | | |
| Mucositis Note: Radiation-related mucositis is graded as Mucositis due to radiation. | Painless erythema, edema, or ulcers preventing swallowing or requiring hydration or parenteral (or enteral) nutritional support | Severe ulceration requiring prophylactic intubation or resulting in documented aspiration pneumonia |
| Typhlitis (inflammation of the cecum) Also consider Hemorrhage/bleeding with grade 3 or 4 thrombocytopenia, Hemorrhage/bleeding without grade 3 or 4 thrombocytopenia, Hypotension, Febrile neutropenia. | Abdominal pain, diarrhea, fever, and radiographic or biopsy documentation | Perforation, bleeding or necrosis or other life-threatening complication requiring surgical intervention (e.g., colostomy) |

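### The background promises to relate treosulfan exposure to toxicity, but adverse-event recording starts at grade 3, so ordinary grade 2 mucositis and lower-grade drug rash are not captured (minor)

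*Combined protocol and SAP*

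**What the plan says.** Section 3C (2d), Treosulfan Pharmacokinetics, gives the reason for sampling. In a cited series of 77 pediatric patients, exposure above 1650 mg*h/L, compared with below 1350, "was associated with an increased risk of developing grade 2 or higher mucositis" (OR 4.40, 95% CI 1.19-16.28). It also carried an "increased risk of skin toxicity, including erythematous rash and skin exfoliation" (OR 4.51, 1.07-18.93) and a higher risk of multiple toxicities (OR 4.52, 1.32-15.53). A grade is given for mucositis only. The section then says the trial will collect samples to see whether exposure "impacts engraftment and both acute and long-term toxicities", and that this will inform later treosulfan studies.

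Section 14B.7 asks for 7 samples on day -6 from each consenting patient, and 7 more on day -5 from those under 4 years. Section 4C lists the PK work as exploratory and names PK parameters only.

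Sections 17C and 17E set what is recorded: "All grade 3 and 4 adverse events (or highly unusual grade 2 adverse events), which occur from the start of study treatment" through day 100, whatever the attribution. Events up to day 30 are assessed separately. On duration, 17E says "The end of the adverse event reporting period occurs through day 100 post-transplant", or when ongoing drug-related or serious events have resolved or stabilised. Appendix G, the grading table named in 17C, has columns for grades 3 and 4 only.

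**The concern.** The finding that motivates the sampling is set at grade 2 or higher for mucositis, and recording starts at grade 3. A child with high AUC and ordinary grade 2 mucositis has no mucositis event in the CRF and looks the same as a child with none. The trial's exposure-toxicity analysis would then rest on fewer events than the study it follows. A null result would be hard to interpret, because absence of an effect could not be told apart from absence of recording. Blood samples cannot be taken again later, so the matching outcome has to be collected alongside them if the stated aim is to be met. The same question arises for long-term toxicity, which the aim includes.

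**Working it through.** The documents give no sample size, endpoint definition or analysis for the exposure-toxicity question, so there is no design figure to reproduce. The check is mainly a comparison of sections.

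**1. The cited figures are coherent.** With SE = [ln(upper) - ln(lower)] / (2 x 1.96) and z = ln(OR)/SE:
- Mucositis: SE 0.667, z 2.22, p 0.0264 (stated 0.026).
- Skin: SE 0.733, z 2.06, p 0.0399 (stated 0.040).
- Multiple toxicities: SE 0.629, z 2.40, p 0.0165 (stated 0.016; the difference is within rounding of the interval).

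**2. Does the grade 2 exception help?** It covers only highly unusual events. Section 15A lists stomatitis/mucositis in children as very common (10% or greater), and erythema, rash and exfoliative dermatitis as common (1-9%). Those lists are not split by grade, but an expected toxicity at ordinary grade 2 is not a highly unusual event.

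**3. Does the grading table help?** The Appendix G mucositis row begins at grade 3: "Painless erythema, edema, or ulcers preventing swallowing or requiring hydration or parenteral (or enteral) nutritional support". Its skin rows are erythema multiforme and GVHD-associated rash. There is no row for drug-related rash or exfoliation. Section 17D supplies CTCAE grades, or adjectives where no criterion exists; that governs how an event is graded, not whether it is entered.

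**4. Is there a separate rule for PK participants?** Sections 4C, 9, 14B.7 and the schedule for all diseases add none. The separate assessment to day 30 in 17C sets no lower threshold.

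**5. After day 100.** Ongoing drug-related events are followed until resolved or stable (17E). CRFs are completed at 6 months, 1 year, 1.5 years and then annually (17J). No item for drug toxicity first appearing after day 100 is specified, and the CRFs are not in the documents. Collection stops, except for death, once a patient goes on to off-protocol treatment after graft failure or recurrence (17E).

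**6. Illustration of the effect on power.** All inputs except the OR are assumptions: 15 or 25 patients per exposure group; grade 2 or higher mucositis in 20% or 40% at low exposure; OR 4.4; 25% or 50% of those events at grade 3 or higher, with the same share in both groups; two-sided 5% level; normal approximation for two proportions.

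At 20%, the odds are 0.25 x 4.4 = 1.10, so the high-exposure rate is 1.10/2.10 = 52%. At 40%, the odds are 0.667 x 4.4 = 2.93, so the rate is 2.93/3.93 = 75%.

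| n per group | Low / high rate, grade 2+ | Power, grade 2+ recorded | Power, half are grade 3+ | Power, a quarter are grade 3+ |
|---|---|---|---|---|
| 15 | 20% / 52% | 0.45 | 0.20 | 0.12 |
| 15 | 40% / 75% | 0.48 | 0.18 | 0.10 |
| 25 | 20% / 52% | 0.67 | 0.31 | 0.17 |
| 25 | 40% / 75% | 0.71 | 0.27 | 0.14 |

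If high exposure also raised the share of events reaching grade 3, the loss would be smaller than shown.

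**The case against.** The exposure-toxicity question is not a listed objective. Section 4C names PK parameters only, sampling is optional, and Section 19 contains no exposure-toxicity analysis. No primary or secondary conclusion and no stopping rule depends on it. This stands, and it is why the point is minor.

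The background does not promise to repeat the cited endpoint at the same threshold, and all grade 3-4 events are recorded from the start of conditioning. This also stands: a reader might infer that the trial cannot study acute toxicity by exposure at all, and that goes too far.

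The Appendix G definition of grade 3 mucositis includes events needing only hydration or nutritional support. Section 3C does not name the scale used in the cited series, so its grade 2 cannot be mapped onto this table. The share of the cited endpoint that is lost is therefore unknown. For skin, no grade is stated at all.

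A reader might also infer that nothing is available after day 100. The documents do not support that: ongoing drug-related events are followed, later CRFs exist, and chronic GVHD, infections, non-relapse mortality at 1 year and survival are secondary objectives. What can be said is only that no new-onset late drug-toxicity item is specified.

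Lower-grade events may be in medical records, since staff at the coordinating center abstract charts (17J). No such abstraction is planned for grade 2 events. Outside sites send CRFs with source documents for eligibility, treatment and serious events, and other outcome sources only when possible. An event of lower grade that met a seriousness criterion would be reported under 17G, but ordinary grade 2 mucositis or rash would not.

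**Conclusion.** The mismatch holds in limited form. Under the written rules, ordinary grade 2 mucositis and lower-grade drug rash are not entered in the CRF. The exposure-toxicity aim in Section 3C (2d) can therefore be pursued only for grade 3-4 acute events, with fewer events and less power, and a null result could partly reflect the recording threshold. It could equally reflect a small PK sample or no true effect.

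The size of the loss cannot be taken from the documents. The power ranges, about 0.45-0.71 against 0.10-0.31, rest on assumed group sizes and rates and show direction only. The conclusion on recording does not depend on them. The long-term part is a gap in specification, not proof of missing data. Severity is minor.

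**What to change.** In 17C and 17E, for patients who give PK samples, record the worst grade (1-4) of mucositis and of skin toxicity from the start of conditioning to day 30, a window 17C already assesses separately. Grade by CTCAE under 17D, because Appendix G has no grade 1 or 2 definitions. Add named late toxicities to the existing 6-month and annual CRFs if they are not already there.

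If this is not wanted, narrow the aim in Section 3C (2d) to engraftment and grade 3-4 events to day 100.

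The first option costs slightly more chart abstraction for PK participants, with no extra visit or sample. The second costs one sentence and gives up the lower-grade and long-term questions.
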